7.3 Conventions

All data listings, summaries, figures and statistical analyses will be generated using SAS version 9.4 or higher¹.

Summaries will be presented by treatment (Treatment 1 and 2). Treatment periods (T1/T2) will be displayed as follows:

--

Treatment 1	Treatment 2	Overall
-------------	-------------	---------

Overall columns are to be included within the table shells as follows:

Demography	Overall
Baseline	Overall
Disposition	Overall
PD	Treatment
AEs	Treatment & overall
Other safety	Treatment

Listings will be sorted in the following order subject, treatment period (T1/T2), parameter, and study day unless otherwise stated.

Continuous variables will be summarized by the number of non-missing observations, mean, median, standard deviation, and minimum and maximum.

Categorical variables will be summarized by presenting the frequency and percent. Percentages will be based on the number of non-missing observations or the subject population unless otherwise specified. For each variable, all categories will be shown. Zero frequencies (but not the percent) within a category will be presented.

7.3.1 Decimal Places

Decimal places for derived data will be determined by the scale of measurement unless otherwise stated. No decimal places will be displayed if the smallest calculated value is ≥ 100 ; 1 decimal place will be displayed when the smallest value is within the interval (10, 100), with 10 being inclusive; 2 decimal places will be displayed when the smallest value is within (1, 10), with 1 being inclusive; and so on for even smaller scales of measurement.

Derived data where it is known in advance the result will be an integer for example day, month, year, number of days and total scores (for rating scales) will be presented with zero decimal places.

Means, medians and percentiles will be displayed to one more decimal place than the data, dispersion statistics (e.g. standard deviation) will have two more decimal places, and the minimum and maximum will be displayed to the same number of decimal places as reported in the raw data. Percentages will be displayed with one decimal place.

P- Values will be quoted to 3 decimal places. P-values < 0.001 will be presented as $p < 0.001$. Where this value is less than 0.05, 0.01 or 0.001, attention will be drawn to this fact using the conventional “*”, “**” or “***” annotation, respectively.

7.4 Derived Variables

7.4.1 Area under the effect curve over 28 days (AUEC28)

AUEC28 days is defined as the change from baseline (for cortisol, glucose, and WBC) and calculated using linear trapezoidal summation from pre-dose to Day 28 in each treatment period.

AUEC28 analyses for the for cortisol, glucose, and WBC will be based on the assumption that the baseline assessment take place at time zero. Only scheduled and ET visit assessments will be included in the computation. If the actual time is not recorded the nominal time will be used. Cortisol, glucose, and WBC ET assessments will be mapped to Day 28 and AUEC28 will then be computed.

If a subject has no pre-dose value, AUEC28 will not be calculated. In the case where a subject has two values recorded at the same time, the two scores will be averaged.

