3.5.2.6 Visit 9 (Treatment 1, Day 15 ± 2 days)

[Redacted text block]

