3.5.2.12 Visit 18 (Treatment 2, Day 15 ± 2 days)

[Redacted text block for Visit 18]

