7.2.5 Unscheduled Visits

Except for ET assessments, only scheduled post-baseline laboratory and vital signs values will be tabulated. Post-baseline repeat/unscheduled assessments will be disregarded, although these post-baseline assessments will be listed in the relevant appendices to the CSR.

For post-baseline PD, laboratory and vital sign data, if an Early Termination assessment falls between two visits and the visit prior to that ET visit has a valid assessment, then that ET assessment will be mapped to the subsequent visit within the treatment period. If the scheduled assessment prior to an ET assessment is missing, then the ET assessment will be mapped to that prior assessment. Assessments from T1 cannot be assigned to T2.

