7.11.1 Dexamethasone-induced HPA suppression

Blood samples for PD will be collected at screening, for T1 at pre-dose (baseline), Days 1, 2, 3, 4, 5, 8, 15, and 28, for T2 at pre-dose (baseline), Days 1, 2, 3, 4, 5, 8, 15 and 28.

Dexamethasone-induced HPA suppression will be evaluated by using the observed plasma cortisol level, blood glucose levels, and WBC count. Plasma cortisol levels, plasma WBC counts, and fasting plasma blood glucose levels will be summarized by treatment group and day using descriptive statistics for observed, change from baseline, and percent change from baseline values. Summary tables will include, the arithmetic mean, standard deviation, coefficient of variation, minimum, maximum, median, and geometric means will also be reported.

[figure not shown]

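### SAP 7.4.1 moves every early-termination cortisol, glucose and WBC value to Day 28, which overstates AUEC28 when the effect recovers after an early sample

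*SAP*

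**What the plan says.** SAP 7.4.1 defines AUEC28 as a linear trapezoid on change from baseline, from pre-dose to Day 28, separately in each treatment period. On sample times it says "If the actual time is not recorded the nominal time will be used", so recorded times are otherwise used. It then makes an exception for early termination: "Cortisol, glucose, and WBC ET assessments will be mapped to Day 28 and AUEC28 will then be computed". No earliest day, window or exclusion is attached.

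SAP 7.2.5 has another ET rule, which opens "For post-baseline PD, laboratory and vital sign data, if an Early Termination assessment falls between two visits". If the preceding visit is valid, "then that ET assessment will be mapped to the subsequent visit within the treatment period". Otherwise: "If the scheduled assessment prior to an ET assessment is missing, then the ET assessment will be mapped to that prior assessment". Neither section refers to the other, and the readable text of SAP 10 does not settle the matter.

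SAP 7.11.1 gives the sampling days, the same in both periods: "for T2 at pre-dose (baseline), Days 1, 2, 3, 4, 5, 8, 15 and 28". The visit headings in Protocol 3.5.2.5, 3.5.2.6, 3.5.2.11 and 3.5.2.12 give the Day 8 and Day 15 visits a window of ± 2 days.

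**The concern.** A cortisol, glucose or WBC value drawn a few days after the injection may still show most of the effect. Placing it at Day 28 treats that effect as lasting up to about three weeks longer than anyone observed.

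AUEC28 is one of the two parameters in the 80-125% rule of SAP 7.11.4 and the only variable in the cortisol paired t-test. Each subject carries weight, because enrolment stops once 12 subjects have had both injections (SAP 5). Someone who leaves early after the second injection still counts among the 12. The PD population in SAP 7.1.3 needs only one usable post-dose result, and its exclusion for major violations is discretionary, so it cannot be relied on to remove such a subject.

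**Working it through.** **Inputs.** From the documents: sampling on Days 1, 2, 3, 4, 5, 8, 15 and 28; 12 pairs; 90% CI on the log scale; limits 80-125%. The documents give no recovery curve, within-subject CV or ET rate, and no AUEC figure to reproduce, so the following are assumptions. Effect as a fraction of baseline:
- a stepped curve with 80/70/50/30/10/0/0% on Days 2/3/4/5/8/15/28, linear between;
- 80% on Day 2, then recovery with half-life 1, 2, 4, 7 or 14 days;
- 80% on Day 2 with no recovery.

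**Step 1: area under 7.4.1.** Area = sum of (t2 - t1) x (y1 + y2)/2. For the stepped curve, the full area is 0.40 + 0.75 + 0.60 + 0.40 + 0.60 + 0.35 + 0 = 3.10 baseline-days. For ET on Day 6, the observed part to Day 5 is 2.15 and the ET value is 0.30 - 0.20/3 = 0.233. Moved to Day 28, it adds 23 x (0.30 + 0.233)/2 = 6.13. The total is 8.28, and 8.28/3.10 = 2.67x. The same calculation on every curve, with Day 15 valid for the Day 20 column:

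| Curve | Full area | ET Day 6 | Day 10 | Days 11-12 | Day 20 |
|---|---|---|---|---|---|
| Stepped | 3.10 | 2.67 | 1.44 | 1.39-1.35 | 1.00 |
| Half-life 1 d | 1.66 | 1.91 | 1.07 | 1.06-1.05 | 1.00 |
| Half-life 2 d | 2.92 | 2.55 | 1.36 | 1.31-1.28 | 1.00 |
| Half-life 4 d | 5.30 | 2.33 | 1.55 | 1.49-1.44 | 1.03 |
| Half-life 7 d | 8.18 | 1.89 | 1.48 | 1.43-1.40 | 1.06 |
| Half-life 14 d | 12.28 | 1.48 | 1.29 | 1.27-1.25 | 1.06 |
| No recovery | 21.2 | 1.00 | 1.00 | 1.00 | 1.00 |

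ET on a scheduled visit day is left out, because 7.2.5 does not cover it.

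**Step 2: area under 7.2.5.** For the stepped curve with ET on Day 6, the value goes to Day 8: 2.15 + 3 x 0.267 = 2.95, or 0.95x. Over all curves and between-visit days from 6 to 14, the area is 0.25-1.10x of the full one. The low end is the no-recovery curve on Days 6-7, where the curve ends at Day 8.

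**Step 3: effect on the T2/T1 ratio.** One T2 area inflated by k among 12 pairs multiplies the geometric mean ratio by k^(1/12).
- Day 6: 1.48 gives 1.033 and 2.67 gives 1.085.
- Day 10: 1.07 gives 1.006 and 1.55 gives 1.037.

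A subject with T1 only also enters the mixed model. Added to 12 pairs, that subject has weight -1/(13(r + 1)) on the log ratio, where r is the between/within variance ratio. For r = 4 to 1 this is -0.015 to -0.038, so the ratio moves by -0.6% to -3.7% (Day 6) or -0.1% to -1.7% (Day 10).

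**Step 4: chance of meeting 80-125% for one parameter.** Simulation of paired log-differences with SD = sqrt(2 ln(1 + CV²)), T2 truly equal to T1, and one T2 area multiplied by k:

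| Within-subject CV | Undistorted | k = 1.4 | k = 2.2 | Subject dropped (n = 11) |
|---|---|---|---|---|
| 15% | 93% | 86% | 47% | 89% |
| 20% | 65% | 58% | 29% | 59% |
| 30% | 16% | 14% | 7% | 13% |

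**Step 5: paired t-test.** Assume a true T2 area 25% larger and an SD of differences of 0.21 of the T1 area. Power is 96% and about unchanged up to 1.6x. It is then 88-90% at 2.0x, 81-84% at 2.2x and 59-61% at 2.67x; the lower figure lets the inflated area keep its variance and the higher holds it fixed. Among the between-visit days examined, only Days 6-7 reach 2x.

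**The case against.** The best defence is that the two sections do different jobs. SAP 7.2.5 sits under unscheduled visits and begins with what is tabulated. SAP 7.4.1 is specific to AUEC28, and the ET visit is Visit 19, which is titled as T2 Day 28. That reading is reasonable, though the SAP does not state it and 7.2.5 names PD data without restriction. It settles precedence only: if 7.4.1 governs, Step 1 is exactly what happens.

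A reader might infer that the rules plainly conflict on all of Days 6-7 and 9-14. The documents do not support that. Days 6-10 fall in the Day 8 window and Days 13-17 in the Day 15 window, so a sample then might count as a scheduled visit at its actual time. Before Day 15, only Days 11-12 lie clearly outside both windows, and there the overstatement is 1.05-1.5x. But a sample labelled ET on any of these days still goes to Day 28 under 7.4.1.

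A reader might also infer that the rule favours a lack-of-effect conclusion, or that T2 follow-up is unprotected. A T2 early leaver works against that conclusion; only a T1-only leaver pushes the ratio down, by at most 3.7%. Protocol 3.5.3 encourages staying to Visit 10 and has no matching sentence for T2. However, Protocol 3.3.4 asks for every effort to complete the EOS/ET assessments whenever a subject stops, and 3.5.3 asks for a return visit.

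It also stands that at a CV of 30% or more the 80-125% rule mostly fails anyway, so one distorted subject changes little.

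**Conclusion.** The point holds as a stated rule that misfires. Placing an early ET value at Day 28 gives a wrong area whenever the effect recovers afterwards, and it does so even if 7.4.1 clearly takes precedence. Falling back on 7.2.5 does not cure it, because that curve may end before Day 28.

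The text of the rule is certain; the sizes are conditional. They rest on assumed curves and CVs and on one early termination within a period. The damage is large only for samples drawn in about the first week, moderate to about Day 14 and small after a valid Day 15. The chance of meeting 80-125% suffers noticeably at CVs of 15-20%. Harm to the t-test needs distortion of about 2x or more. The documents do not show that any conclusion of this trial would change.

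**What to change.** Replace the sentence in SAP 7.4.1 with:

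> For AUEC28, ET samples are used at their actual collection time; the mapping in 7.2.5 applies to by-visit summaries only. If the last sample in a period is before a pre-specified day (for example Day 13, the start of the Day 15 window), AUEC28 is missing for that period in the main analysis. If it is on or after that day and there is no sample in the Day 28 window, its change from baseline is held flat to Day 28.

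On the same curves the flat extension gives 0.98-1.20x of the full area for last samples on Days 13-25. Also:

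- State whether an ET sample inside a visit window counts as that scheduled visit.
- Add a sensitivity analysis that computes both areas over the same truncated interval for each T2 early leaver.
- State that a planned Visit 19/EOS after T1 Day 28, in a subject not re-injected (Protocol 3.5.2.8), is not an ET value for T1 AUEC28. Otherwise it could be averaged with the real Day 28 value.

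The cost is wording and one table, with no new data. Day 13 is a judgement. Dropping a subject loses more than it gains when distortion is below about 1.28x (CV 15%), 1.37x (CV 20%) or 1.46x (CV 25%), and ET on Days 11-12 can fall there. Missing areas may be informative, hence the sensitivity analysis, but that analysis misses differences arising after the last sample. With half-life 4 days in T1 and 7 in T2, the full ratio is 8.18/5.30 = 1.54, but it is 1.12 truncated at Day 6 and 1.24 at Day 10.

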7.4.2 Maximum Effect (Emax)

Emax is the maximum increase from baseline (pre-treatment level, T1 or T2) in glucose level and WBC count or the maximum decrease in cortisol levels over the 28 days post dose in each treatment period. An Emax value will be calculated for cortisol, glucose, and WBC for each treatment period (T1/T2).

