7.2 Baseline

Unless otherwise specified, baseline is defined as the last non-missing measurement taken prior to treatments T1 or T2 (reference start date). This includes screening or unscheduled assessments that would have been performed no earlier than 21 days before the reference start date.

In the case where the last non-missing measurement and the reference start date coincide, that measurement will be considered pre-reference, but AEs and medications commencing on the reference start date will be considered post-reference.

For laboratory tests, baseline is defined as the last measurement obtained during screening prior to T1.

For vital signs parameters, an assessment performed on reference start date with time point marked as “pre-dose” will be considered as baseline for the given treatment period.

Baseline ECG is the last measurement prior to the index injection.

For physical exams, baseline is defined as the last assessment prior to T1 on Day 0.

For General and Targeted Neurological Exam baseline for each treatment period is defined as the pre-dose assessment.

For cortisol suppression, glucose, and white blood cell counts, baseline is defined as the last non-missing value obtained prior to T1 or T2, which is T1/T2 Day 1 pre-dose measurement.

For NPRS and BPI-SF, baseline is defined as the last non-missing value obtained prior to T1 or T2, which is T1/T2 Day 0 measurement.

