7.11.4 Area under the effect curve over 28 days and maximum effect

The area under the effect curve over 28 days (AUEC28) and maximum effect (Emax) following the T1 (index) and T2 (repeat) injections will be calculated for cortisol levels, WBC counts, and fasting blood glucose levels.

AUEC28 will be compared for cortisol following index and repeat injections within the same subject to conclude whether or not repeat injection results in more pronounced cortisol suppression. This will be done using a two-sided paired T-test with the null mean being zero.

AUEC28 and Emax will be compared for cortisol, glucose, and WBC between index injection (treatment 1) and repeat injection (treatment 2) using a mixed model analysis of variance using PROC MIXED with a fixed effect for treatment (treatment 1 and 2) and a random effect for subject. Estimates and 90% confidence intervals (CIs) will be first constructed in the logarithmic scale. The response variable will be the change from pre-dose of each PD parameter. Treatment comparisons will be performed between treatments T1 and T2 with T2 being the reference. By taking anti-logarithms, estimates and CIs for the geometric means and ratios of geometric means will be calculated. All CIs will be 2-sided.

The statistical model will have the following form:

The following SAS code will be used to run the model;

[REDACTED]

The following SAS code will be used to calculate the geometric means, geometric ratio and its confidence interval:

```
[REDACTED SAS CODE]
```

A lack of effect of repeat injection on the PD will be concluded if the 90% CIs for the ratio of T2 (repeat injection; Test) to T1 (index; Reference) for both AUEC28 days and Emax are completely contained within the range of 80 to 125%.

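### Cortisol Emax is capped by the pre-dose value, so its limb of the 80–125% rule progressively loses sensitivity to deeper suppression after the repeat injection once T1 suppression exceeds about 80%

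*SAP*

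**What the plan says.** - **Measure.** SAP 7.4.2 defines cortisol Emax as "the maximum decrease in cortisol levels over the 28 days post dose in each treatment period". SAP 7.11.4 confirms the scale: "The response variable will be the change from pre-dose of each PD parameter". It is an absolute fall, not a percentage and not the nadir. Protocol 5.2.7 has the same definition.
- **Baseline.** SAP 7.2 gives each period its own cortisol baseline, "which is T1/T2 Day 1 pre-dose measurement".
- **Decision rule.** SAP 7.11.4 states: "A lack of effect of repeat injection on the PD will be concluded if the 90% CIs for the ratio" of T2 to T1, "for both AUEC28 days and Emax are completely contained" within 80 to 125%. The intervals come from a mixed model on the log scale: "Estimates and 90% confidence intervals (CIs) will be first constructed in the logarithmic scale". Protocol 5.2.7 has the same rule.
- **Separate cortisol test.** SAP 7.11.4 also compares cortisol AUEC28 between injections, to judge whether the second one suppresses cortisol more: "This will be done using a two-sided paired T-test with the null mean being zero". Emax has no such test.
- **Other cortisol output.** SAP 7.11.1 summarises observed, change and percent-change values by treatment and day, descriptively only.
- **Sample size.** SAP 5 sets 12 subjects completing both injections, without a power calculation.

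**The concern.** The primary objective concerns HPA suppression after repeat dosing, so the direction that matters is deeper or longer suppression at T2. An absolute decrease has a ceiling at the pre-dose value. Once the first injection has removed most of the cortisol, little room is left for the second to show a larger decrease, however much lower the nadir goes. A ratio within 80–125% could then be reported as lack of effect on this limb while the lowest cortisol had fallen several-fold. No planned inferential comparison uses the nadir or the percentage of pre-dose cortisol remaining.

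**Working it through.** The plan has no power or precision figure to reproduce. The steps below derive the ceiling and then pass it through the CI rule.

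**Inputs from the documents.** Emax is the decrease from the period's own pre-dose value (SAP 7.4.2, 7.2). The rule uses a two-sided 90% CI on the log scale within 80–125% (SAP 7.11.4). There are 12 completers (SAP 5). The limits are reciprocal (1/1.25 = 0.80), so it does not matter here that one sentence of SAP 7.11.4 names T2 as the reference and the decision rule names T1.

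**Assumed, because not in the readable text.** Within-subject CV of Emax from 5% to 30%; complete pairs; log-normal variation.

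**1. The ceiling.** Let B1 and B2 be the pre-dose values and f1 and f2 the fractions suppressed, each at most 1.

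Ratio T2/T1 = (B2 × f2)/(B1 × f1) ≤ (B2/B1)/f1

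With complete pairs the ratio of geometric means is the geometric mean of the subject ratios, so the bound carries over with B2/B1 and f1 read as geometric means.

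With B1 = B2 the largest possible ratio is:
- 1/0.80 = 1.250
- 1/0.85 = 1.176
- 1/0.90 = 1.111
- 1/0.95 = 1.053

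**2. Unequal pre-dose values.** The true ratio can no longer exceed 1.25 once f1 ≥ 0.8 × (B2/B1). That threshold is 64% at B2/B1 = 0.8, 72% at 0.9, 80% at 1.0, 88% at 1.1 and 96% at 1.2. Above B2/B1 = 1.25 there is none. A lower T2 pre-dose value can therefore hide deeper suppression even when T1 suppression is below 80%. A higher one can push the ratio above 1.25 with no deeper suppression.

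**3. Illustration.** Take a pre-dose value of 15 units in both periods. At 90% suppression the nadir is 1.5 and Emax is 13.5. At 98% the nadir is 0.3 and Emax is 14.7. The nadir is five-fold lower, and the Emax ratio is 14.7/13.5 = 1.089.

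**4. Through the CI rule.** For n = 12 the 90% limits are the estimate times exp(±1.796 × SD_diff/√12), with SD_diff = √2 × √ln(1 + CV²). The table gives the percentage of 100,000 simulated trials in which the Emax CI lies within 80–125%, with equal pre-dose values.

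| Suppression T1 → T2 | True ratio | CV 5% | 10% | 15% | 20% | 25% | 30% |
|---|---|---|---|---|---|---|---|
| 75% → 98% | 1.307 | 0 | 0.4 | 0.9 | 1.5 | 1.8 | 1.7 |
| 80% → 100% | 1.250 | 5.0 | 5.0 | 4.9 | 5.1 | 4.5 | 3.4 |
| 85% → 98% | 1.153 | 98.1 | 58.7 | 34.7 | 23.7 | 15.5 | 8.5 |
| 90% → 98% | 1.089 | 100 | 93.6 | 67.9 | 45.3 | 26.2 | 12.8 |
| 95% → 99% | 1.042 | 100 | 99.4 | 86.8 | 60.2 | 33.0 | 15.4 |
| 90% → 90% | 1.000 | 100 | 100 | 92.5 | 65.4 | 35.3 | 16.1 |

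From about 90% T1 suppression, the deeper-suppression rows approach the no-change row. At CV 20%, the 90% → 98% trial fails in 55% of runs, but the trial with no change fails in 35%.

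**5. CV needed to fail at the ceiling.** If the observed ratio sits exactly at its cap, the upper limit passes 1.25 only when the CV exceeds about 8% (f1 = 85%), 16% (90%) or 24% (95%).

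**6. AUEC28.** It is also built from change from baseline. If T2 raises the suppressed fraction by the same factor at every time point, with equal pre-dose values, the AUEC28 ratio is that same factor: 0.98/0.90 = 1.089.

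**The case against.** The strongest reply is that the rule judges an interval, not a point estimate. This stands. A reader might infer that, from 80% T1 suppression, the limb cannot respond to deeper suppression or can fail only through baseline variation. The documents do not support that, because the CI must be "completely contained within the range of 80 to 125"%. At exactly 80% with complete T2 suppression the limb fails in about 95% of runs, and between 80% and about 90% a drug-driven shift clearly raises the failure rate. Nor does near-complete suppression guarantee a pass on repeatable baselines: with a true ratio of 1, only 35% of runs pass at CV 25%.

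A second reply is that other parts of the plan cover the question, and this stands in part. Both AUEC28 and Emax must meet the rule, so passing Emax alone concludes nothing. AUEC28 can register longer suppression, and its paired t-test is aimed at stronger suppression. The daily summaries show depth and recovery for both periods. But AUEC28 is bounded by baseline in the same way for depth, and the summaries carry no T2/T1 comparison. A reader might infer that Emax should be replaced or that a recovery-time analysis is required. AUEC28 already responds to duration, and the documents give no recovery percentage on which to base such an analysis.

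Third, the expected depth of suppression is not in the readable text, so the ceiling may not matter in practice. This also stands and makes the point conditional.

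**Conclusion.** The point holds as a loss of sensitivity, not as an absolute block. With equal pre-dose values the true cortisol Emax ratio cannot exceed 1.25 once T1 suppression is at least 80%; in general the threshold is 0.8 × (T2/T1 pre-dose ratio). The loss grows above that and is marked from about 90%, where a five-fold lower nadir meets the Emax criterion in 94% of simulated trials at CV 10% and 68% at 15%. Failures well above 80% mostly reflect imprecision or baseline variation. The ceiling follows from the definition alone. The pass rates rest on the assumed CVs, 12 complete pairs and equal pre-dose values. Whether the ceiling matters in practice depends on the depth of T1 suppression, which the readable text does not give. It does not invalidate the decision rule, but an added depth measure is a worthwhile, inexpensive improvement.

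**What to change.** In SAP 7.11.4:

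1. Keep Emax as planned for all three markers; no change is needed for glucose and WBC.
2. For cortisol, add the T2/T1 geometric mean ratio with 90% CI of the lowest post-dose cortisol, or of the lowest percentage of pre-dose remaining. State in advance how values below the assay limit are handled.
3. Report the T2/T1 ratio of the pre-dose cortisol values next to it.
4. State that a cortisol Emax ratio within 80–125% will not by itself be read as evidence against deeper suppression when T1 suppression is at or above 0.8 × (T2/T1 pre-dose ratio), that is, 80% with equal pre-dose values.

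The cost is some SAP text and one or two tables from samples already scheduled, with no added visits. The downside is that the nadir is noisier near the assay limit, and a lack-of-effect claim becomes somewhat harder to support.
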